### 4.4 Blinding.

The three acupressure formulas (relaxing, stimulating and sham) will be labeled acupressure set "A", set "B", and set "C". Acupressure educators, outcome assessors, study participants, and study investigators (who will not interact with any of the study participants) will be blinded as to acupressure allocation. Only after data analysis is completed will the randomization code be unblinded. Those randomized to usual care will know that they are not receiving acupressure.

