### 4.5 Intervention Methods.

We will teach participants to perform acupressure on themselves, i.e., self-administered acupressure. The participants will be taught by acupressure educators who are study staff, and who will be trained by the study co-PI [name], a professional acupuncture practitioner. Training will include basic philosophy of TCM and acupressure, demonstration of acupressure points (relaxing, stimulating or sham points). He will designate the three sets of points as set "A", set "B", or set "C" so educators will be blinded as to which sets of points are the true versus the sham treatment. He will also ask the educators to demonstrate the correct location, pressure and stimulation techniques.

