### 4.5.3 Relaxing Acupressure

There are 5 acupoints with 4 of the acupoints performed on both the left and right sides of the body (total of 9 points to stimulate; see Figure 3.0). Each of the 9 acupoints will be stimulated for 1 minute per point giving a total treatment time of 9 minutes daily. The relaxing acupoints are:

- Point 1: Yin tang (Unilaterally)
- Point 2: Anmian (EX17) (Bilaterally)
- *Point 3*: Heart 7 (HT7) (Bilaterally)
- Point 4: Spleen 6 (SP6) (Bilaterally)
- Point 5: Liver 3 (LV3) (Bilaterally)

4.5.3.1 Justification for the Choice of Relaxing Acupressure Points. The "True Acupressure" points were chosen based on a TCM theory for treating insomnia, that these specific acupoints are commonly used for insomnia in clinical trials, that previous studies using these 5 specific acupressure points found better results than other commonly used acupressure points for inducing sleepiness, and mechanistic studies indicating effects on sleep for the 4 of the 5 acupoints: HT-7; SP-6; LV-3; and *anmian*, which have demonstrated effects on sleep-related neurotransmitter systems and HPA axis activity in basic, human and animal studies.

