#### 4.5.4 Stimulating Acupressure

Stimulating acupoints were chosen to increase daytime activity. There are 6 acupoints with 4 of the acupoints performed on both the left and the right sides of the body giving a total of 10 points to stimulate. Each of the 10 acupoints will be stimulated for 1 minute per point giving a total treatment time of 10 minutes done once daily. The acupoints are:

- Point1: Si Shen Chong (Unilaterally)
- Point2: Conception Vessel 6 (CV6)
- Point 3: Large Intestine 4 (LI4) (Bilaterally)
- Point 4: Stomach 36 (ST36) (Bilaterally)
- Point 5: Spleen 6 (SP6) (Bilaterally)
- Point 6: Kidney 3 (K3) (Bilaterally)

4.5.4.1 Justification for the Choice of Stimulating Acupressure Points Acupoints were chosen by consensus of 4 acupressure practitioners and based on a previous study design in students with sleep disturbances as well as TCM theory for treating insomnia and fatigue. Practitioners had all been in practice for at least 2 years actively seeing patients. They also had been trained as and received one of more of the following degrees; a Naturopathic Doctorate (ND), masters in TCM or Oriental Medicine and a license of acupuncture (L.Ac.) or a diploma in acupuncture (Dipl. Ac.). Practitioners were asked to choose a set of relaxing and stimulating acupressure points based on a Western diagnosis of fatigue that could be reasonably reached by participants,

i.e., not the middle of the back, and not so many points that it would take an excessive amount of time to complete a treatment.

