### 4.5.5 Sham Acupressure

Sham acupoints were chosen by [name] in locations where no known acupoints exists. There are 5 acupoints with 4 of the acupoints being performed bilaterally (Figure 5.0). None of these points are on meridians nor are they near actual points (at least one inch away from meridians). They were chosen to be in the same general body quadrant as the true points. Each of the 9 acupoints will be stimulated for 1 minute per point giving a total treatment time of 9 minutes daily. The sham acupoints are:

- Pressure Point #1 (Unilaterally)
- Pressure Point #2 (Bilaterally)
- Pressure Point #3 (Bilaterally)
- Pressure Point #4 (Bilaterally)
- Pressure Point #5 (Bilaterally)

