### 4.7.3 Interim phone call- Participant Interaction #2 (within 2 weeks, +/- 2 weeks)

A phone call by study team will be conducted to assess adherence, AEs, BFI or to otherwise answer questions.

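### Section 4.4 claims a blind with no exception, but the co-PI sets the A/B/C code, the point sets carry cues for educators, and the BFI shares contacts with adherence and fidelity checks

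*Combined protocol and SAP*

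**What the plan says.** Section 4.4 labels the three formulas A, B and C and lists four blinded roles: educators, outcome assessors, participants, "and study investigators (who will not interact with any of the study participants) will be blinded as to acupressure allocation". The code is to be opened only after the analysis. Usual-care participants openly know their status. Section 4.0 calls the trial single-blind.

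Section 4.5 says the educators are study staff "who will be trained by the study co-PI". Of the same person it says "He will designate the three sets of points as set" A, B or C, "so educators will be blinded as to which sets of points are the true versus the sham treatment".

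On the sets themselves:
- Section 4.5.3 (relaxing) includes "Point 4: Spleen 6 (SP6) (Bilaterally)".
- Section 4.5.4 (stimulating) includes "Point 5: Spleen 6 (SP6) (Bilaterally)".
- Section 4.5.5 says of the sham points: "None of these points are on meridians nor are they near actual points". It also places them in the same general body areas as the true points.

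On outcome collection, section 4.7.3 reads "A phone call by study team will be conducted to assess adherence, AEs, BFI", and the schedule in 4.6 marks both adherence and BFI at week 2. Section 4.7.4 puts the BFI, the fidelity check and the blinding check in one week-6 interaction. No section says who takes the BFI or in what order.

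**The concern.** The primary measure, the BFI, is rated by the participant, and each participant is taught one to one. Whoever knows which set is sham could pass on expectation, even without meaning to. The contrasts with usual care are open, so the comparison of true with sham acupressure is the masked contrast that bears on efficacy beyond expectation. That comparison depends on the blind that 4.5 promises for educators.

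Three things look out of line with 4.4. An investigator holds the key to the letters. The make-up of the sets offers educators clues. The person taking the BFI may learn the arm, or see the set performed, in the same contact. The plan assesses blinding once, at week 6, and describes no check of the educators. A report that repeated 4.4 would claim a blind that the plan itself does not secure.

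**Working it through.** This is mainly a comparison of sections, with a small count.

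**1. The co-PI.** Section 4.4 blinds investigators without exception. Section 4.5 has the co-PI assign the letters. Whoever assigns a code knows its meaning, so the two statements cannot both hold for him. Knowing the key is one step short of knowing allocation: he would also need a participant's letter, or results by letter. Section 4.3 gives the randomization scheme to the statistician, and 4.4 says investigators do not meet participants. But no section withholds letters or by-letter results from him, and 10.3.2 has the whole research team meet monthly.

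**2. The sets.** Points = one-sided + 2 × two-sided, at 1 minute per point (4.5.3 to 4.5.5):
- relaxing: 1 + 2 × 4 = 9 points, 9 minutes
- stimulating: 2 + 2 × 4 = 10 points, 10 minutes
- sham: 1 + 2 × 4 = 9 points, 9 minutes

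These reproduce the plan's own figures. The acupressure arms hold 3 × 18 = 54 participants, 18 of them on the stimulating set (4.3).

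*Cue one, point count.* With no information, each letter is guessed correctly with chance 1/3, and so is the sham letter. An educator who knows that the stimulating set has 10 points names that set for certain and guesses between the other two. The expected share of letters correct is (1 + 1/2 + 1/2)/3 = 2/3. The chance of picking sham is 1/2. Count alone does not separate relaxing from sham.

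*Cue two, overlap.* SP6 is in both true sets, on both sides of the body, and no sham point is near an actual point. The two true sets therefore share a location, and sham shares none with either. An educator who reasons that the overlapping sets are the true ones has found sham, and the count then tells stimulating from relaxing. Acupoint names are not needed, because educators learn locations. Matching sham on minutes and body area does not remove this cue.

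**3. BFI contacts after randomisation** (4.6, 4.7.3 to 4.7.5):

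| Week | Also in the same contact | What it can reveal |
|---|---|---|
| 2 | adherence, AEs | acupressure versus usual care |
| 6 | adherence, fidelity, AEs, logbook | the same, and the set itself when points are demonstrated |
| 10 | AEs | little, unless bruising is raised |

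Two of the three BFI assessments therefore share a contact with a check that applies only to the acupressure arms.

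**The case against.** The best defence is that 4.4 blinds people to who received which formula. Holding the key is not the same as holding the list, and no section says the co-PI sees a participant's letter. That stands as far as it goes. It does not rescue a statement that makes no exception for the key-holder and sets no barrier.

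On educators, relaxing and sham are well matched: 5 acupoints, 9 points, 9 minutes, same body areas. A reader might infer that the make-up reveals sham for all 54 acupressure participants. The documents do not support that. It would need every educator to learn all three sets, notice the overlap and draw the conclusion. The training text in 4.5 does not state outright that each educator learns all three, and 4.5.1 speaks of two interventions. Educators' prior knowledge is not given.

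A reader might also infer that handouts name true points and merely number sham points. That contrast is in the protocol's own lists; the handouts are not shown.

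On the week-2 call, adherence reveals acupressure versus usual care, not the letter, and 4.4 can fairly be read as covering the formula only. Section 4.7.3 lists the BFI after adherence and AEs, but a list is not an asking order. The BFI is participant-rated, so the caller's knowledge adds a limited risk to a contrast that is already open. Week 6 is the stronger example.

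Two further readings go too far. True versus sham is not the only contrast protected from expectation, since relaxing versus stimulating is masked too. The co-PI is not shown to judge AEs or remove participants: 10.3.2 and 7.1 give those roles to the PI.

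Finally, this is an exploratory pilot, which limits the consequence but does not make the statement in 4.4 accurate.

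**Conclusion.** The point holds in three parts of differing strength.

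- **Firm:** the blinding statement is inaccurate for the co-PI, who cannot be blind to the meaning of the letters, and no barrier to letters or by-letter results is written.
- **Vulnerable, not shown to fail:** educators necessarily know the set they teach and are masked only to true versus sham. Point count can identify the stimulating set (18 of 54) and raises the chance of picking sham from 1/3 to 1/2. Adding the SP6 overlap could identify sham outright. This assumes that the educator learns all three sets, notices the overlap and, to name the two true sets, knows that stimulating is the longer one.
- **Factual, smaller:** at weeks 2 and 6 the BFI shares a contact with adherence or fidelity checks, with no order or separate assessor stated.

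The documents give no size for an expectation effect, so no bias can be computed. The claim is that the stated blind is not secured as written, not that results would be biased by a known amount.

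**What to change.** 1. In 4.4, name the co-PI as unmasked to the A/B/C key. Keep him from participants' letters, by-letter results and analysis decisions until the code is opened.
2. In 4.4, state that educators know the assigned set, are masked only to true versus sham, and may have cues (the 10-point set and the shared point).
3. Use neutral point labels, such as Point 1 and Point 2, and one common teaching script for all three sets, whatever the present materials use.
4. At weeks 2, 6 and 10, have the BFI self-completed where possible and always before any adherence, fidelity, AE or logbook question.
5. Record each educator's guess of what A, B and C are, alongside the existing week-6 blinding check.

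A separate BFI collector is not asked for, because staffing is not documented. Order alone does not help if the person taking the BFI also trained that participant; self-completion is the protection there.

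The cost is protocol wording, minor changes to forms and a less favourable blinding statement. No visits or participants are added.

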### 4.5 Intervention Methods.

We will teach participants to perform acupressure on themselves, i.e., self-administered acupressure. The participants will be taught by acupressure educators who are study staff, and who will be trained by the study co-PI [name], a professional acupuncture practitioner. Training will include basic philosophy of TCM and acupressure, demonstration of acupressure points (relaxing, stimulating or sham points). He will designate the three sets of points as set "A", set "B", or set "C" so educators will be blinded as to which sets of points are the true versus the sham treatment. He will also ask the educators to demonstrate the correct location, pressure and stimulation techniques.

### 4.5.1 Testing Fidelity of the Intervention in Acupressure Educators

[name] will test the acupressure educators after their first two participants and thereafter once every three months. He will also ask them to identify each acupoint for both interventions, apply the correct amount of pressure and stimulation on a point on himself; and ask them how long to stimulate each point, and how often points should be stimulated. Incorrect answers will be addressed and corrected. Further, acupressure educators can request additional clarification and instruction at any time. Acupressure educators achieved a 92% fidelity score in our previous study.

### 4.5.2 Teaching Participants the Acupoints

From our previous study participants can be taught to perform their acupoints within 15 minutes. Acupressure educators will meet with each participant separately and demonstrate the location of each acupoint on themselves and on the participants. Participants will be given an illustration of acupoints along with a written description of where the points are located. At the end of the session participants will be tested to determine their acupressure fidelity by demonstrating the location of all their acupoints to the educator and appropriate adjustments will be made. Acupressure educators also demonstrate on the participant the appropriate level of pressure to apply and the correct motion. Participants are asked to stimulate points on the educator until it is determined that they are using the correct pressure. Participants may return at any time to be retrained or ask clarifying questions.

### 4.5.3 Relaxing Acupressure

There are 5 acupoints with 4 of the acupoints performed on both the left and right sides of the body (total of 9 points to stimulate; see Figure 3.0). Each of the 9 acupoints will be stimulated for 1 minute per point giving a total treatment time of 9 minutes daily. The relaxing acupoints are:

- Point 1: Yin tang (Unilaterally)
- Point 2: Anmian (EX17) (Bilaterally)
- *Point 3*: Heart 7 (HT7) (Bilaterally)
- Point 4: Spleen 6 (SP6) (Bilaterally)
- Point 5: Liver 3 (LV3) (Bilaterally)

4.5.3.1 Justification for the Choice of Relaxing Acupressure Points. The "True Acupressure" points were chosen based on a TCM theory for treating insomnia, that these specific acupoints are commonly used for insomnia in clinical trials, that previous studies using these 5 specific acupressure points found better results than other commonly used acupressure points for inducing sleepiness, and mechanistic studies indicating effects on sleep for the 4 of the 5 acupoints: HT-7; SP-6; LV-3; and *anmian*, which have demonstrated effects on sleep-related neurotransmitter systems and HPA axis activity in basic, human and animal studies.

#### 4.5.4 Stimulating Acupressure

Stimulating acupoints were chosen to increase daytime activity. There are 6 acupoints with 4 of the acupoints performed on both the left and the right sides of the body giving a total of 10 points to stimulate. Each of the 10 acupoints will be stimulated for 1 minute per point giving a total treatment time of 10 minutes done once daily. The acupoints are:

- Point1: Si Shen Chong (Unilaterally)
- Point2: Conception Vessel 6 (CV6)
- Point 3: Large Intestine 4 (LI4) (Bilaterally)
- Point 4: Stomach 36 (ST36) (Bilaterally)
- Point 5: Spleen 6 (SP6) (Bilaterally)
- Point 6: Kidney 3 (K3) (Bilaterally)

4.5.4.1 Justification for the Choice of Stimulating Acupressure Points Acupoints were chosen by consensus of 4 acupressure practitioners and based on a previous study design in students with sleep disturbances as well as TCM theory for treating insomnia and fatigue. Practitioners had all been in practice for at least 2 years actively seeing patients. They also had been trained as and received one of more of the following degrees; a Naturopathic Doctorate (ND), masters in TCM or Oriental Medicine and a license of acupuncture (L.Ac.) or a diploma in acupuncture (Dipl. Ac.). Practitioners were asked to choose a set of relaxing and stimulating acupressure points based on a Western diagnosis of fatigue that could be reasonably reached by participants,

i.e., not the middle of the back, and not so many points that it would take an excessive amount of time to complete a treatment.

### 4.5.5 Sham Acupressure

Sham acupoints were chosen by [name] in locations where no known acupoints exists. There are 5 acupoints with 4 of the acupoints being performed bilaterally (Figure 5.0). None of these points are on meridians nor are they near actual points (at least one inch away from meridians). They were chosen to be in the same general body quadrant as the true points. Each of the 9 acupoints will be stimulated for 1 minute per point giving a total treatment time of 9 minutes daily. The sham acupoints are:

- Pressure Point #1 (Unilaterally)
- Pressure Point #2 (Bilaterally)
- Pressure Point #3 (Bilaterally)
- Pressure Point #4 (Bilaterally)
- Pressure Point #5 (Bilaterally)

#### 4.5.6 Usual Care (UC)

Participants will be asked to continue following their healthcare providers' instruction for chronic SLE management. We anticipate that most women will be treated per the American College of Rheumatology clinical guidelines. Participants will be asked to continue any current treatment and not to start or stop treatments including acupuncture/acupressure over the course of the study. All treatments for pain will be recorded.

### 4.6 Study Schedule and Contacts

	SCREENING	TREATMENT PHASE		FOLLOW-UP		
Week	-2 to 0 (+/- 2 weeks)	0 (+/- 2 weeks)	1-6	2 (+/- 2 weeks)	6 (+/- 2 weeks)	10 (+/- 2 weeks)
Activity	Participant Interaction #0	Participant Interaction #1 Baseline	Daily (Days 1 to 42)	Participant Interaction #2 Phone Call	Participant Interaction #3 Post-Treatment	Participant Interaction #4 Follow-up Call/Visit
Informed Consent		х				
Comorbidities	X					
Medication and Health History		х				
Sociodemographics	x					
Concomitant Medications		x			X	X
Lupus Activity (SLAQ) 	X	Х			X	X
BFI 	X	х		x	x	X
CSQ 	x					
ARPHI 	x					
PHQ9 	x					
Promis Fatigue 8 Item		х			x	Х
RAND SF-36 		x			X	X
PSQI 		X			X	X

\* = bilateral

IPAQ		x				Х
GAD7 		х			х	X
PANAS 		х			х	X
SWLS 		х			х	x
Fibromyalgia Survey Criteria		х			х	х
Perform Acupressure			X		x	
Assess Treatment Fidelity		x			x	
Assess Blinding					x	
Adverse Events				x	х	х
Adherence to Acupressure			x	x	х	
BPI 		х			х	х
Logbook			x			
1. SLAQ = Systemic Lupus Activity Questionnaire; CSQ – Connective Tissue Screening Questionnaire; ARPHI –Authorization for Protected						
Health Information; BFI = Brief Fatigue Inventory; PHQ9 = Patient Health Questionnaire 9-Item; PSQI = Pittsburgh Sleep Quality Index; IPAQ=						
International Physical Activity Questionnaire; GAD7 = Generalized Anxiety Disorder 7-Item; PANAS = Positive and Negative Affect Schedule;						
SWIS = Satisfaction With Life Scale: BPI = Brief Pain Inventory						

### 4.7 Study Visits

#### 4.7.1 Screening- Participant Interaction #0 (to determine eligibility)

A screening phone call will be made to evaluate participant interest and eligibility including, comorbidities and ability to maintain a stable lifestyle over the course of the study. Sociodemographic and participant contact information will be collected. Fatigue will be assessed using the Brief Fatigue Inventory (BFI) and baseline depression and lupus disease activity status with the Patient Health Questionnaire 9 (PHQ-9) and the Systemic Lupus Activity Questionnaire (SLAQ). If a potential participant is not a part of the U of M health system they will complete the Connective Tissue Screening Questionnaire (CSQ) and will be sent an Authorization for Release of Protected Health Information form to complete and give to their health care provider.

### 4.7.2 Randomization/Baseline- Participant Interaction #1 (Week 0, +/- 2 weeks)

Written informed consent will be obtained at the beginning of the study visit. Medication and health history, concomitant medications, lupus disease activity and urine pregnancy test results will be collected if applicable. Participants will complete BFI, SLAQ, PROMIS Fatigue Short Form 8 (PROMIS Fatigue 8), RAND SF-36, Pittsburg Sleep Quality Index (PSQI), the Brief Pain Inventory (BPI), Generalized Anxiety Disorder 7 (GAD7), The Satisfaction With Life Scale (SWLS), Fibromyalgia Survey Criteria (FM Survey Criteria), International Physical Activity Questionnaire (IPAQ) and The Positive and Negative Affect Schedule (PANAS). Participants will be instructed in how to perform their acupressure and told to start their acupressure on the following day. Participants will complete the Acupressure Fidelity test after the acupressure instruction has been completed. A study logbook will be dispensed, to document conduct of acupressure and the time of day. The post-treatment visit will be scheduled for exactly six weeks from the start day and the follow-up visit for four weeks post termination of treatment.

### 4.7.3 Interim phone call- Participant Interaction #2 (within 2 weeks, +/- 2 weeks)

A phone call by study team will be conducted to assess adherence, AEs, BFI or to otherwise answer questions.

### 4.7.4 Post-Treatment- Participant Interaction #3 (Week 6, +/- 2 weeks)

Participants return to study site or we will conduct the interaction via BlueJeans or Skype. BFI, SLAQ, PROMIS Fatigue 8, RAND SF-36, PSQI, BPI, GAD7, SWLS, FM Survey Criteria, and PANAS will be conducted. Any adverse events or change in medication will be collected. Treatment fidelity and blinding will be assessed; study

logbooks will be collected and participants will be asked to stop performing acupressure. If participants choose to conduct the visit using BlueJeans or Skype they will email or mail their logbooks in and pressure will be assessed by observing nail blanching as an indicator of correct pressure.

